8.5.1 Analysis Population

The statistical analysis of efficacy will include all patients completing the initial treatment with vismodegib alone and start the concurrent vismodegib with radiation therapy. Anyone who receives any vismodegib with radiation therapy will be included in the assessment of efficacy. As the most conservative approach, any patient removed from study prior to completion of at least 75% of radiation therapy without a documented complete or partial response will be considered as a case of local-regional failure.

Failure is defined as a lack of local-regional control within the boundaries of the treated radiation PTV area within the 12 month follow-up period.

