2.3.2 Secondary Endpoints

- Estimate of the probability of PFS, with failure defined as any disease recurrence or death due to any cause, and OS with each duration measured from the time of first treatment with vismodegib to 12 months after completion of study treatment.
- The number and attribution of all adverse events, (including vital signs, physical findings, and clinical laboratory results, CTCAE, v 4.0) in patients who receive any amount of study drug and radiation therapy at any point during protocol therapy or during the followup period.
- The proportion of any adverse events (CTCAE, v. 4.0) assessed to be definitely, probably, or possibly related to vismodegib or its combination with radiation therapy at any point during protocol therapy or during the followup period.
- The proportion of patients experiencing Grade 4-5 adverse events assessed to be definitely, probably, or possibly related to the induction or concurrent treatment components of the protocol regimen (that is not definitely related to disease progression) at any point during protocol therapy or during the followup period.
- The proportion of patients discontinuing treatment due to toxicity during the concurrent administration of vismodegib and radiation therapy (<75% of planned radiation therapy delivered).
- Response rate (as per RECIST) of the primary site and regionally involved areas following all treatment components at 3 months after the completion of protocol therapy.

- Proportion of patients with a decrease of BCC within the irradiated planning tumor volumes (PTV) in patients who complete initial combined therapy, indicating a clinical response to vismodegib and radiation therapy.

3 Study Design

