6.1.2.2 Study Procedures, Week 13-14 (End of Induction)

Within 14 days after completion of induction vismodegib therapy, patients must have a re-evaluation to determine if there has been disease progression prior to starting concurrent treatment. Patients whose disease has progressed will no longer continue on study.

- Physical examination including weight
- Vital signs
- Performance status
- Evaluation of adverse events
- Concomitant medications
- Skindex-16 survey
- Laboratory assessments
 - Hematology
 - Serum chemistries
- Urine or serum pregnancy tests - if a woman of childbearing age
- Disease assessment
- Imaging (CT or MRI) of head and neck for tumor assessment
- CT chest or chest x-ray – if clinically indicated
- For externally visible tumors
 - Bidimensional measurements of externally visible tumor dimension
 - Standardized digital photography of target lesion(s)

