6.1.5 Long Term/Survival Follow-up Procedures

The study team will follow patients for survival outcome via telephone calls or medical record requests approximately every 3 months for 12 months, until death or loss to follow-up, whichever occurs first. Additional, survival follow-up information may be collected via telephone calls and/or at clinic visits every 3 months for 12 months. Follow-up may consist of at least a telephone contact with the patient, a family member, or physician to inquire about the patient's survival status.

If/when a subject begins a new type of non-protocol treatment for laBCC or mBCC, long-term follow up may cease. Subjects will continue to be followed if they have not recurred local-regionally within the original treated PTV. If they have a BCC in a non-treated separate location, or if metastatic disease occurs, subjects will continue to be followed for the local-regional disease control outcomes. Subjects would be taken off protocol if they have any form of non-protocol treatment affecting the primary local or nodal site that was originally treated or if they receive vismodegib or other Hedgehog inhibitor or chemotherapy outside of original protocol parameters. Patients off study protocol who need to have vismodegib will not have drug provided by the study.

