7.2.1.1 Definitions

Evaluable for toxicity

All patients receiving any study drug will be evaluable for toxicity from the time of their first treatment with the study drug.

Evaluable for objective response

Only those patients who have measurable disease present at baseline, have completed at least 75% of protocol-mandated radiotherapy, and have had their disease re-evaluated will be considered evaluable for response. These patients will have their response classified according to the definitions stated below. (Note: Patients who exhibit objective disease progression prior to the end of induction therapy will also be considered evaluable.)

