The duration of overall CR is measured from the time measurement criteria are first met for CR until the first date that recurrent disease is objectively documented.

Duration of stable disease

Stable disease is measured from the start of the treatment until the criteria for progression are met, taking as reference the smallest measurements recorded since the treatment started.

Progression-Free Survival

Progression-free survival (PFS) is defined as the duration of time from start of treatment to time of progression or death due to any cause.

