8.3.2 Replacement Policy

Patients who drop-out before starting radiation therapy will be replaced. In addition, patients who come off study before completing at least 75% of radiation therapy given concurrently with vismodegib without grade ≥ 3 toxicity will be replaced. The frequency of each of these events will be reported and reasons for replacement reviewed.

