The secondary clinical aims of the duration of progression free survival (PFS) and overall survival (OS) will be measured from the start of protocol therapy until death due to any cause or until the first evidence of any disease progression, or death, respectively. Point estimates (e.g. median, percent PFS at 12 months) with 95% confidence intervals will be calculated using the Kaplan-Meier product limit method to summarize results. Based upon RECIST criteria, the proportion of patients responding in the primary site and regionally involved areas at 3 months after completing protocol therapy will be determined and presented with 95% confidence intervals. The proportion of patients achieving any decrease in BCC within the boundaries of the treated radiation PTV area will be determined and presented with a 95% confidence interval. In addition, the proportion of patients who start concurrent vismodegib and radiation therapy and receive at least 75% of the planned radiation therapy will be determined and presented with a 95% confidence interval to summarize the feasibility of administering concomitant therapy.

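### PFS and OS run from the first vismodegib dose, but the only efficacy population is patients who start radiotherapy; applied as written, this would leave induction failures out of PFS

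*Combined protocol and SAP*

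**What the plan says.** **Time origin.** Sections 2.2 and 2.3.2 have PFS and OS "measured from the time of first treatment with vismodegib to 12 months after completion of study treatment". Under Response Criteria (7.2.1.4), "Progression-free survival (PFS) is defined as the duration of time from start of treatment to time of progression or death due to any cause". Section 8.5 also starts both clocks at the beginning of protocol therapy and uses Kaplan-Meier, with no landmark or delayed entry.

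**Population.** Section 8.5.1 is the only place that defines an efficacy set: "The statistical analysis of efficacy will include all patients completing the initial treatment with vismodegib alone and start the concurrent vismodegib with radiation therapy". The set of patients with at least one dose appears only for safety (7.4, 8.6).

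**What lies between.** Section 5.1 and Table 5.1 put about 12 weeks of induction, then up to 14 days, before RT. At the end-of-induction re-evaluation (6.1.2.2), "Patients whose disease has progressed will no longer continue on study". Section 8.3.2 replaces patients who drop out before RT.

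**Text that pulls the other way.** Section 7.2.1.1 notes that "Patients who exhibit objective disease progression prior to the end of induction therapy will also be considered evaluable", but under the heading for objective response.

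**Horizon.** Section 8.5 says "Point estimates (e.g. median, percent PFS at 12 months) with 95% confidence intervals will be calculated", on a curve that starts with therapy. Sections 2.2, 2.3.2 and 8.2 set the horizon at 12 months after therapy is completed.

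**The concern.** To enter the 8.5.1 set a patient must live, and for the most part remain progression-free, until RT begins. If that set is used for a curve whose clock starts at the first dose, the induction weeks are credited to patients selected for having come through them. Patients who failed in those weeks never appear. This is guaranteed-time bias, and for PFS it can only run in the favourable direction.

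Induction is part of the regimen under study, so progression or death during it is a failure of that regimen. At stake is the credibility of the reported PFS. OS has the same mismatch in a weaker form: deaths in induction would be omitted, but a patient removed alive for progression affects OS only through later survival.

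**Working it through.** **The plan's own figure.** Section 8.3.1 gives 24 evaluable patients, 60% against 80%, directional 0.10, exact binomial, 81% power. Requiring at least 18 of 24 successes gives type I error 0.096 and power 0.811. Requiring 17 would give type I error 0.192, so 18 is the cutoff. The 81% reproduces. It concerns local-regional control and does not involve PFS or OS, for which no design figure is stated.

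**Length of the guaranteed time.** 12 to 14 weeks × 7 / 30.44 = 2.8 to 3.2 months.

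**Is that time fully event-free?** Not quite.
- Section 6.1.5: "If they have a BCC in a non-treated separate location, or if metastatic disease occurs, subjects will continue to be followed". A new lesion at an untreated site could therefore count as a PFS event without stopping RT.
- Section 7.1 leaves termination of therapy to a benefit-risk judgement when metastases look likely, although such lesions count as progression.

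A patient of either kind could have an event in induction and still be in the RT-starter set, where the event would be counted.

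**Size of the bias.** Let f be the share of dosed patients whose progression or death keeps them from starting RT. Without other losses, for any time t after RT start:

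S_all(t) = (1 − f) × S_RT(t), so S_RT(t) / S_all(t) = 1 / (1 − f).

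The documents give neither f nor an expected PFS. Assume 24 RT starters, a reported PFS of 70% and k induction failures, so that f = k / (24 + k):
- k = 0: f = 0, all-dosed PFS 70.0%, no bias
- k = 1: f = 1/25 = 4.0%, 0.70 × 24/25 = 67.2%, difference 2.8 points
- k = 2: f = 2/26 = 7.7%, 0.70 × 24/26 = 64.6%, difference 5.4 points
- k = 3: f = 3/27 = 11.1%, 0.70 × 24/27 = 62.2%, difference 7.8 points

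**Event-free withdrawals.** Add two withdrawals to the case k = 2.
- Censored before the failures: 0.70 × (1 − 2/26) = 64.6%
- Censored after them: 0.70 × (1 − 2/28) = 65.0%
- All four losses wrongly counted as events: 0.70 × (1 − 4/28) = 60.0%

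Only true events belong in f, and censoring the rest barely moves the estimate.

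**Against sampling error.** The approximate 95% half-width at 70% and n = 24 is 1.96 × √(0.7 × 0.3 / 24) = 0.183, or 18 points.

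**Horizon (separate point).** Twelve months from therapy start is about week 52. Twelve months after a 21-week course is about week 21 + 52 = 73. The scheduled 12-month visit is counted from the End of Treatment visit at weeks 29 to 33 (6.1.4, Table 6.1), so it falls near weeks 81 to 85.

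**The case against.** The strongest reply is that 8.5.1 was written for local-regional control. After its opening sentences it deals only with failure within the irradiated volume, and it never names PFS or OS. It says whom the analysis will include, without an explicit restriction to those patients. Section 8.5 names RT starters for the feasibility proportion but not for PFS or OS, so an all-dosed analysis is a tenable reading. That stands as far as it goes: a reader might infer that PFS in this trial will be biased, and the documents do not support so firm a statement. Bias requires both that 8.5.1 governs PFS and that some dosed patient fails before RT. Yet the sentence covers the efficacy analysis without limit and no other set is offered. If only local-regional control was meant, PFS and OS have no stated population, and the same addition is needed.

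The note in 7.2.1.1 on induction progressors does not settle the matter, because it concerns response only and does not match 8.5.1.

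A reader might also take a size from the protocol's background. In the phase I study (1.2.1), 4 of 33 patients with BCC, or 12.1%, progressed on vismodegib alone. That group mixed locally advanced and metastatic disease and has no time window. The median PFS figures in 1.2.2 come from metastatic patients and from locally advanced patients in whom radiotherapy had failed or was contraindicated. Neither gives f for this regimen.

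Finally, these are descriptive endpoints, and the illustrated shifts lie within the 18-point half-width. Section 8.3.2 also promises that "The frequency of each of these events will be reported and reasons for replacement reviewed". All true, but a confidence interval does not show a systematic shift, and 8.3.2 does not say whether induction progressors count as drop-outs.

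**Conclusion.** The concern holds in conditional form. If 8.5.1 is applied to PFS as written, events that keep dosed patients from starting RT are left out and PFS is overstated by 1/(1−f). With 24 RT starters and an assumed reported 70%, that is about 3, 5 or 8 points for one, two or three such failures, and nothing if there are none. These are illustrations, not estimates for this trial. They assume that f counts only events that prevent RT and that event-free withdrawals are uninformative. OS is affected only through deaths in induction or worse later survival among those removed.

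A reader might infer that the primary result is also undermined. This point does not support that: the primary test and its 81% power do not depend on the PFS and OS population. The change is worth making because the stated rule can give a wrong answer in the favourable direction and the PFS remedy is cheap.

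**What to change.** 1. State in 8.5.1 that PFS and OS are estimated from first dose in all patients who receive at least one dose of vismodegib, the set already used in 8.6. Count progression (PFS) or death (PFS and OS) during induction as an event on its date, and censor event-free withdrawals.
2. Start any curve restricted to RT starters at the first RT fraction and label it conditional on reaching RT.
3. Reconcile the evaluability note in 7.2.1.1 with 8.5.1, and say in 8.3.2 whether induction progressors are among the reported drop-outs.
4. For OS, reconcile the follow-up text. Section 6.1.2.2 takes induction progressors off study, 6.1.5 lets long-term follow-up cease once non-protocol treatment begins, and 7.1 makes information on removed progressors voluntary. The text should make clear that survival calls continue for these patients; otherwise they are censored at last contact and this is reported.
5. As a separate minor edit, align the 12-month PFS example in 8.5 with the horizon in 2.2, 2.3.2 and 8.2, noting that follow-up visits count from the End of Treatment visit.

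**Cost.** For PFS it is a few sentences, since the week 13-14 disease assessment is already scheduled; estimates may become slightly less favourable. For OS there is real but modest work in keeping contact with patients removed in induction. Dose and sample size do not change.

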8.3 Determination of Sample Size and Accrual Rate

8.3.1 Sample Size and Power Estimate

The sample size for this single-arm phase II study is based upon the anticipated degree of improvement in the primary clinical hypothesis (i.e. local-regional control rate) at 12 months after completing all protocol treatment. The null hypothesis is that 60% of patients treated may achieve local-regional control after treatment on the study. Patients treated for advanced-stage

nonmelanomatous skin cancers typically achieve 50-60% local-regional control with radiation therapy alone. The alternative hypothesis is that 80% of the patients will obtain local-regional control at 12 months from the end of protocol therapy. This goal for local-regional control is justifiable as the current study includes radiation therapy, which is known to be effective against advanced BCC, in combination with vismodegib, also known to have high efficacy against BCC when administered alone.

Sample Size Justification: With accrual of 24 evaluable patients, this test will have 81% power to detect an increase in the overall proportion of patients achieving local-regional control assuming a directional level of significance of 0.10 based upon a one sample exact binomial test. It is anticipated that accrual will be completed in 12-18 months, with each patient treated for approximately 5.5 months and then followed for 12 months after completing protocol therapy. The total study duration is expected to be about 3 years.

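### The primary test leaves out patients who fail during vismodegib induction, while its 60% null comes from radiation alone; the sections that decide who counts conflict

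*Combined protocol and SAP*

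**What the plan says.** Section 8.1 describes the treatment under study as vismodegib alone followed by vismodegib with radiation, so induction belongs to the regimen being judged. Six places then decide who counts in the primary result.

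- Section 8.5.1 fixes who enters the efficacy test: "The statistical analysis of efficacy will include all patients completing the initial treatment with vismodegib alone and start the concurrent vismodegib with radiation therapy".
- Section 8.5 (Analyses Plans) scores as a local-regional failure a patient who begins concurrent therapy and is removed before 75% of radiation without a documented response. Section 8.5.1 repeats the rule for any patient removed before that point, but within the population it has just defined.
- Section 6.1.2.2, on the re-evaluation after induction: "Patients whose disease has progressed will no longer continue on study".
- Section 7.2.1.1, on evaluability for objective response: "Patients who exhibit objective disease progression prior to the end of induction therapy will also be considered evaluable".
- Section 8.3.2: "Patients who drop-out before starting radiation therapy will be replaced". No reason for leaving is named. The grade 3 toxicity condition appears only in the next sentence, on patients who leave before 75% of radiation.
- Section 3.2 puts both kinds of exit into one sentence, so the grade 3 toxicity condition can be read as applying to pre-radiation exits too. It also defines the 24 evaluable patients as completing at least 75% of radiotherapy.

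Section 8.3.1 takes its null from experience that advanced "nonmelanomatous skin cancers typically achieve 50-60% local-regional control with radiation therapy alone".

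**The concern.** Leaving during induction because the tumour grew, because the drug was not tolerated or because of death is an outcome of the regimen. If those patients drop out of the denominator and are not scored as failures, the test estimates control among patients who got through induction. The comparison figure is justified by radiation alone, with no induction step described. Removing early failures from one side only pushes the observed rate up.

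At stake is the meaning of a positive result. A reader would take it to say that the whole regimen beats 60%. It could arise with no gain among all patients who start vismodegib, at a probability above the stated one-sided 0.10.

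**Working it through.** **1. The plan's own figure.** Inputs from section 8.3.1: n = 24; "The null hypothesis is that 60% of patients treated may achieve local-regional control after treatment on the study"; "The alternative hypothesis is that 80% of the patients will obtain local-regional control at 12 months from the end of protocol therapy"; "assuming a directional level of significance of 0.10 based upon a one sample exact binomial test". Let X be binomial.

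- P(X ≥ 17 | 24, 0.60) = 0.192, above 0.10.
- P(X ≥ 18 | 24, 0.60) = 0.096, so the cut-off is 18 of 24.
- P(X ≥ 18 | 24, 0.80) = 0.811.

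The stated 81% power is reproduced. The issue is the denominator, not this calculation.

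**2. How an induction failure is handled.**

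- *Progression found at re-evaluation.* Section 6.1.2.2 takes the patient off study, so radiation never starts and 8.5.1 leaves the patient out. If progression came before the end of induction, 7.2.1.1 calls the patient evaluable. Two denominators result.
- *Toxicity stop or death before radiation.* Section 8.5.1 leaves the patient out, and the failure rule in 8.5 does not apply because concurrent therapy never began. Section 7.2.1.1 does not mention these patients.
- *Replacement.* For a pre-radiation exit with grade 3 or higher toxicity, 8.3.2 reads as replaced and 3.2 can be read as not replaced. The patient is outside the 8.5.1 set either way.

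**3. Sensitivity without assuming a loss rate.** Start from the smallest positive result and add k induction failures to the denominator. The exact p-value is P(X ≥ 18 | 24 + k, 0.60).

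- k = 0: 18/24 = 75.0%, p = 0.096
- k = 1: 18/25 = 72.0%, p = 0.154
- k = 2: 18/26 = 69.2%, p = 0.226

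**4. Chance of a positive result under assumed loss.** Let π be true control among all who start vismodegib, with pre-radiation exits counted as failures, and d the share lost before radiation. The documents do not give d, so 5%, 10% and 20% are assumptions. The rate among radiation starters is π/(1 − d), and the chance of a positive test is P(X ≥ 18 | 24, π/(1 − d)).

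| d | Starter rate, π = 0.60 | P(≥18/24) | Starter rate, π = 0.55 | P(≥18/24) |
|---|---|---|---|---|
| 5% | 0.632 | 0.161 | 0.579 | 0.065 |
| 10% | 0.667 | 0.263 | 0.611 | 0.116 |
| 20% | 0.750 | 0.607 | 0.688 | 0.339 |

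The design value is 0.096.

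**5. The same gap from the other side.** If radiation starters reach 80%, the rate among all who started is 0.80 × (1 − d): 76%, 72% and 64%. At n = 24 with the cut-off of 18, the power of an all-treated test is P(X ≥ 18 | 24, 0.76) = 0.651, P(X ≥ 18 | 24, 0.72) = 0.474 and P(X ≥ 18 | 24, 0.64) = 0.182.

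**The case against.** The best defence is the endpoint itself. Control is defined within the irradiated planning volume, 12 months after therapy is completed (sections 2.1, 2.3.1 and 8.2). A patient who was never irradiated has no such volume, so a radiation-starter set fits the endpoint as written. This stands: an induction exit can be a failure only by assignment. It is a good reason to keep that set for the powered test, but not to let the result speak for everyone who started the regimen.

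Second, the plan is not silent. Section 8.3.2 reports how often patients are replaced and why, section 8.6 covers safety in everyone dosed, and PFS runs from the start of treatment. None of this enters the primary test.

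Third, the failure rule in 8.5.1, read literally, could reach a patient removed during induction. Its place inside the restricted population and the explicit wording in 8.5 point the other way, but the text is not clean.

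Fourth, moving the primary test to all treated patients within 24 would leave 65%, 47% or 18% power at 5%, 10% or 20% loss, and would contradict the definition of the 24 in section 3.2. This stands, and the fix respects it.

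A reader might also infer more than the documents support:

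- *Every induction failure is replaced, whatever the cause.* Section 8.3.2 names no causes, section 3.2 may exempt grade 3 or higher toxicity, and no section says outright that progressors are replaced.
- *Exclusion of progressors is settled.* Section 7.2.1.1 points the other way; this is a contradiction.
- *The radiation-alone patients were unselected.* Section 8.3.1 does not say how they were chosen or counted, only that they had radiation alone.
- *The phase I result in section 1.2.1, 4 of 33 BCC patients progressing, gives the expected loss.* That group mixed metastatic and locally advanced disease, received several doses, and is reported without an exposure time.

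**Conclusion.** The concern holds in a limited form. As written, sections 8.5 and 8.5.1 do not count induction progression, toxicity stops or deaths as failures in the primary test, and the surrounding sections disagree on evaluability and replacement. The direction of the effect is clear: the tested rate is at least as high as the rate among all who start vismodegib when those exits are counted as failures.

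The size is not known. It depends on an induction loss that the documents do not give and on true control among all starters. The 61% figure should not be read as the trial's error rate: it needs both a 20% loss and true control at the top of the cited 50–60% range. At 55% control and 5% loss, the chance of a positive result is below the nominal 0.10. The firmest number needs no loss rate: at this sample size, a single uncounted induction failure is enough to reverse a just-positive conclusion.

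**What to change.** 1. Reconcile sections 3.2, 6.1.2.2, 7.2.1.1, 8.3.2, 8.5 and 8.5.1 so that one denominator applies to the primary test. State for progression, toxicity and death before radiation whether the patient is evaluable, whether replaced, and how scored.
2. Keep the radiation-starter set for the powered test. State in 8.5.1 that its claim is limited to patients who complete induction and start radiation.
3. Add to 8.5 a required companion analysis in all patients who received vismodegib: the proportion with local-regional control, an exact confidence interval, and an exact binomial test against 60%. Count induction progression, treatment-related discontinuation and death before radiation as local-regional failures. Fix in advance how exits for other reasons are handled, and report the companion beside the primary result.

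**Cost.** Wording changes and one further proportion from data the trial already collects, with no added patients. The companion rate will be less favourable if anyone fails during induction. Its power is below 81%: about 65% at 5% loss and 47% at 10% if radiation starters reach 80%, evaluated at n = 24. It therefore guards against over-reading the primary result and does not replace the powered test.
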